2.2 Secondary objectives

The secondary objectives are to assess the clinical course and outcome of adults with COVID-19 who have been treated with Remdesivir with respect to the following:

1. a 7-point ordinal clinical status scale on Day 7 and Day 14
2. timing (from first symptoms and from hospitalisation) and duration of use of Remdesivir
3. clinical severity at Day 7, 14, 28 as assessed by the NEWS 2 score
4. clinical status as assessed a 7-point ordinal scale on Day 28 (or at last observation if discharged or died prior to this time point) in those still hospitalised after Day 14.
5. SpO₂ > 94% on room air on day 7, 14 and 28
6. duration and type (low versus high flow) of oxygen therapy (days)
7. admitted to ICU (yes versus no)
8. number of days spent on ICU/ITU
9. use of mechanical ventilation/ECMO (extracorporeal membrane oxygenation); start and stop dates
10. re-admission with COVID-19 complications or recurrence within 28 days of discharge and outcome (discharged or deceased)

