5 TRIAL PROCEDURES

Only real-world retrospective data will be used for this study. Deidentified retrospective data will be extracted at each clinical site from source data. No personal identifiable data will be transmitted to NEAT ID. Data will be extracted/transcribed in to the eCRF database with standard formatting from electronic medical record (EMR) databases, clinical registries, case series or additional sources from sites/ countries. The data elements will be extracted/transcribed from source data according to the following schedule. Mechanisms to ensure data quality and integrity will be deployed as per applicable standard operating procedures.

	Day1 (Hospital Admission)	Day7 (+/- 1 day) and Day14 (+/- 2 days) / last observation if discharged or died prior to these time points.	Day 28 or last observation after Day 14 if discharged or died prior to this time point.
Medical History ^a	X		
Pregnancy test	X		
HIV test	X		
Vital Signs ^b	X	X	X
Laboratory Testing ^c	X	X	X
Oxygenation ^d	X	X	X
Clinical Status ^e	X	X	X
Other Treatments for COVID-19 ^f	X	X	X
NEWS SCORE ^g	X	X	X

- a. Focused medical history and also the following information (e.g. demographics including ethnicity, baseline characteristics including DM, CV disease and COPD)
- b. SpO₂, body temperature, body weight and height on admission
- c. Includes white blood cell count, creatinine, total bilirubin, ALT, AST at admission Day 7 and day 14 or at discharge if before day 14, radiographic findings at baseline and as available and SARS-CoV-2 pcr, antigen and/or antibody testing.
- d. Includes oxygen supplementation: room air, low flow O₂ (L/min and %), high flow O₂ (L/min and %), non- invasive

positive pressure ventilation (FiO2 or %), mechanical ventilation (FiO2 or %), ECMO (extracorporeal membrane oxygenation)

- e. The ordinal scale is as: 1. Death, 2. Hospitalised, on invasive mechanical ventilation or ECMO, 3. Hospitalised, on non-invasive ventilation or high flow oxygen devices, 4. Hospitalised, requiring low flow supplemental oxygen, 5. Hospitalised, not requiring supplemental oxygen - requiring ongoing medical care (COVID-19 related or otherwise), 6. Hospitalised, not requiring supplemental oxygen - no longer requires ongoing medical care, 7. Not hospitalised

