4.2 Study Variables

All the study variables are summarized in the following table.

	Day1 (Hospital Admission) baseline	Day 7 (+/- 1 day) and Day14 (+/- 2 days) / last observation if discharged or died prior to these time points.	Day 28 or last observation after Day 14 if discharged or died prior to this time point.
Medical History ^a	x		
Pregnancy test	x		
HIV test	x		
Vital Signs ^b	x	x	x
Laboratory Testing ^c	x	x	x
Oxygenation ^d	x	x	x
Clinical Status ^e	x	x	x
Other Treatments for COVID-19 ^f	x	x	x
NEWS SCORE ^g	x	x	x

a. Focused medical history and also the following information (e.g. demographics including ethnicity, baseline characteristics including DM, CV disease and COPD)

b. SpO2, body temperature, body weight and height on admission

c. Includes white blood cell count, creatinine, total bilirubin, ALT, AST at admission Day 7 and day 14 or at discharge if before day 14, radiographic findings at baseline and as available and SARS-CoV-2 PCR, antigen and/or antibody testing.

d. Includes oxygen supplementation: room air, low flow O2 (L/min and %), high flow O2 (L/min and %), non-invasive positive pressure ventilation (FiO2 or %), mechanical ventilation (FiO2 or %), ECMO (extracorporeal membrane oxygenation)

e. The ordinal scale is as: 1. Death, 2. Hospitalised, on invasive mechanical ventilation or ECMO, 3. Hospitalised, on non-invasive ventilation or high flow oxygen devices, 4. Hospitalised, requiring low flow supplemental oxygen, 5. Hospitalised, not requiring supplemental oxygen - requiring ongoing medical care (COVID-19 related or otherwise), 6. Hospitalised, not requiring supplemental oxygen - no longer requires ongoing medical care, 7. Not hospitalised

f. These include corticosteroids, anticoagulants, azithromycin/other antibiotics, anti-inflammatory agents (e.g. Tocilizumab), investigational agents (eg hydroxychloroquine) and immunotherapies such as convalescent plasma and monoclonal antibodies.

g. NEWS 2 score is based on Respiration rate (per minute), SpO2 (%) Air or oxygen. Systolic blood pressure (mmHg), Pulse (per minute) Consciousness, Temperature (°C)

For the purpose of the analyses, partial dates will be extrapolated. For example, all dates saved as NK/FEB/2020 will be recoded as 15/FEB/2020 and those saved NK/NK/2020 will be recoded as 15/JUNE/2020. NK means not known.

5. Sample Size calculation

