6.1 Timing of Analyses

An interim analysis is planned to be performed in June 2021.

The final analysis will be performed in July-September 2021.

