Endpoints	9.1. Time (days) from first symptom to use of Remdesivir 9.2. Time (days) from hospitalization to use of Remdesivir 9.3. Duration (days) of use of Remdesivir
Analysis population	
 Full population analysis
Descriptive statistics and graphical representation	
 Data will be summarized with median and 95% confidence interval globally and according to disease severity at baseline (ORDSC score 2 vs 3-4 vs 5) LogRank test will be used to compared the 3 groups P-values will be two-tailed with a significant level at 5% Kaplan-Meier curves will be plotted.
Statistical analysis	
Kaplan-Meier method will be used to calculate the medians and the 95% confidence intervals of the time to use of Remdesivir. Time (days) from first symptom to use of Remdesivir will be defined by the time between the date of first symptom and the start date of Remdesivir. The event will be the exposure to Remdesivir therapy at least one time during the hospitalization period
 
The time (days) from hospitalization to the use of Remdesivir will be estimate using the Kaplan-Meier method as well as the 95% confidence interval. The event will be the first use of Remdesivir.
 
Duration (days) of use of Remdesivir will be estimated using the Kaplan-Meier method. The time is defined as the time between the start date of Remdesivir and the end date of Remdesivir. The event will be the discontinuation of the use of Remdesivir.

Endpoints	10.1. Frequency of re-admission with COVID within 28 days of discharge 10.2. Frequency of discharge after re-admission 10.3. Frequency of death after re-admission
Analysis population	
 For 10.1, the analysis population will be all subjects who discharge from hospital within the first 28 days For 10.2 and 10.3, the analysis population will be all re-admitted subjects
Descriptive statistics and graphical representation	Data will be summarized with number of subjects with an event out of the total number of analyzed population Data will be summarized globally and according to disease severity at baseline (ORDSC score 2 vs 3-4 vs 5) Chi square test will be used to compared the 3 groups P-values will be two-tailed with a significant level at 5%

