Statistical analysis	The frequency will be estimated by the number of events divided by the total number of analyzed population. . The associated two-sided 95% exact confidence intervals will be calculated using Clopper–Pearson method

11. Reporting Conventions

P-values ≥ 0.001 will be reported to 3 decimal places; p-values less than 0.001 will be reported as “ <0.001 ”. The mean, standard deviation, and any other statistics other than quantiles, will be reported to one decimal place greater than the original data. Quantiles, such as median, or minimum and maximum will use the same number of decimal places as the original data. Estimated parameters, not on the same scale as raw observations (e.g. regression coefficients) will be reported to 3 significant figures.

12. Technical Details

Data will be analysed using the IBM SPSS® statistics software version 24, Stata® SE software version 13 and SAS® software version 9.4.

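### Re-admission is counted over 28 days from discharge, but no collection is specified for that window and the crude proportion has no rule for incomplete windows, so endpoint 10.1 may be undercounted

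*SAP*

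**What the plan says.** - **Objective.** Protocol 2.2, item 10, asks for "re-admission with COVID-19 complications or recurrence within 28 days of discharge and outcome (discharged or deceased". SAP section 9 carries this forward as endpoint 10.1, "Frequency of re-admission with COVID within 28 days of discharge", and SAP Table 2 has matching rows. The clock starts at discharge.
- **Denominator.** SAP 9: "For 10.1, the analysis population will be all subjects who discharge from hospital within the first 28 days". Later discharges are left out.
- **Estimator.** SAP 9: "The frequency will be estimated by the number of events divided by the total number of analyzed population", with a Clopper–Pearson interval and a chi-square comparison of baseline ordinal score 2 vs 3-4 vs 5.
- **Schedule.** Protocol 5, Protocol Appendix 1 and SAP 4.2 print the same table. Its first column is "Day1 (Hospital Admission) baseline" in the SAP version and its last is "Day 28 or last observation after Day 14 if discharged or died prior to this time point". It has no post-discharge time point and no re-admission row. Protocol 5 makes the table the basis for extraction: "The data elements will be extracted/transcribed from source data according to the following schedule". SAP 4.2 presents it as covering every study variable.
- **Timing.** SAP 6.1: "An interim analysis is planned to be performed in June 2021". The final analysis is set for July to September 2021. Protocol 4.1 gives an earliest hospitalisation date (after 31 August 2020), and neither document gives a latest one.

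**The concern.** The endpoint and the schedule run on different clocks: one counts 28 days from discharge, the other ends 28 days from admission. Nobody who leaves hospital after admission can have 28 post-discharge days inside the schedule, and a Day 28 discharge has none. The estimator does not repair this. A patient whose records were never searched after discharge stays in the denominator as a non-event. The SAP's other follow-up endpoints are handled differently: mortality (8.1) and the ICU, oxygen and ventilation frequencies (8.2) are censored at the last observation. SAP 8.1 also lets follow-up for death end at discharge, so nothing elsewhere in the plan implies observation beyond it.

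Endpoints 10.1 to 10.3 are the only ones dedicated to what happens after patients go home. As planned, a low published re-admission rate could not be told apart from records that were not searched. If severity groups differ in when they are discharged, the chi-square test could also pick up differences in observed time rather than in risk.

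**Working it through.** The documents give no re-admission rate, length of stay or sample-size calculation, so there is no planned figure to reproduce. The check compares the two windows and then sizes the gap under labelled assumptions.

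**1. Length of the window.** Admission is Day 1. For discharge on Day d, the endpoint window ends on Day d + 28. The latest discharge in the denominator is d = 28, so the window reaches Day 28 + 28 = Day 56. The schedule ends at Day 28.

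**2. Three readings of what is collected.**
- (a) The schedule taken literally: a discharged patient's last observation is at discharge. Captured share is 0% in every group, so there is no gradient and no usable endpoint.
- (b) Discharged patients are observed to exactly Day 28. Captured share depends on d.
- (c) Re-admission is looked up separately for the full 28 days. Captured share is 100%.

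The documents do not say which applies.

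**3. Size under reading (b).** Days seen: w = 28 − d. Captured share with uniform timing: w/28. Captured share with front-loaded timing (assumption: truncated exponential, 7-day half-life, k = ln 2/7): (1 − exp(−kw))/(1 − exp(−28k)). The denominator is 1 − 1/16 = 0.9375.

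| Discharge day | Days seen | Uniform | Front-loaded | A true 10% would appear as |
|---|---|---|---|---|
| 7 | 21 | 21/28 = 75% | 0.875/0.9375 = 93% | 7.5% or 9.3% |
| 14 | 14 | 14/28 = 50% | 0.75/0.9375 = 80% | 5.0% or 8.0% |
| 21 | 7 | 7/28 = 25% | 0.5/0.9375 = 53% | 2.5% or 5.3% |
| 28 | 0 | 0% | 0% | 0% |

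**4. The severity comparison under reading (b).** All inputs here are assumptions: 400 discharged patients, split 30/300/70 or 60/250/90 across scores 2, 3-4 and 5; discharge days 21/12/7 or 25/14/7; the same true risk, 5% or 10%, in every group.
- Example (30/300/70, days 21/12/7, 10%, uniform): expected events are 30 × 0.025 + 300 × 0.0571 + 70 × 0.075 = 0.75 + 17.1 + 5.25 = 23.1, against 40 with full windows.
- Over all combinations, expected events fall from 40 to about 20–34 (true 10%) or from 20 to about 10–17 (true 5%).
- At a true 10% in every group, score 2 shows 1.1–5.3% and score 5 shows 7.5–9.3%.
- The SAP's chi-square test (2 df, two-tailed 5%), simulated 40,000 times per combination, rejects in 4–25% of runs. With full windows it rejects in 4.5–5.0%.

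**5. Calendar time.** This applies even under reading (c). Day 56 falls 55 days after admission. With an assumed data cut on 30 June 2021, a Day 28 discharge has a complete window only if admission was by 6 May 2021. No last admission date or minimum look-back secures this.

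**6. After the fix.** With 28 post-discharge days searched for everyone in the denominator, captured share is 100% in each group and the expected proportion equals the true risk.

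**The case against.** The strongest reply is that a missing row does not show missing collection. The schedule also has no row for remdesivir start and stop dates, discharge date, ICU days or ventilation dates, yet all of these feed endpoints. Re-admission is a named objective with its own rows in Table 2, and in a retrospective study a site can look past Day 28 in its own records. This stands: the undercount is possible, not shown.

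A reader might go further and infer that re-admissions will be undercounted, most of all in the sickest patients. The documents do not support that. A gradient needs reading (b) together with later discharge in score 2. The second is plausible, but no length of stay is given. Under readings (a) and (c) there is no gradient, and some combinations in step 4 show no excess rejection. The SAP also states that it tests no formal hypothesis.

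Two other apparent faults fall away. Counting a death after discharge as no re-admission is not an error when windows are complete: the crude proportion then equals the cumulative incidence with death as a competing event. A re-admitted patient still in hospital is correctly in neither 10.2 nor 10.3, and the remainder follows by subtraction.

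The calendar argument is also limited. SAP 6.1 does not say that the interim reports this endpoint. A patient admitted by the SAP date of 7 May 2021 reaches Day 56 by 1 July 2021 (7 May plus 55 days), early in the period for the final analysis.

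The reply leaves one thing unanswered: neither document says how far re-admission is searched, and the stated estimator treats unsearched time as event-free.

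**Conclusion.** The point holds as a conditional one. The plan defines a 28-day post-discharge endpoint, specifies no collection over that window, and uses an estimator that scores unobserved time as no re-admission. Endpoint 10.1 may therefore be too low, and the severity comparison may be distorted if groups are discharged at different times.

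The size cannot be fixed from the documents. Captured share is 0% if observation stops at discharge and up to 100% if records are searched far enough. Between these, the 75/50/25/0% figures rest on observation stopping at exactly Day 28 and on uniform risk; front-loaded risk softens them to 93/80/53/0%. Every figure for the severity groups rests on assumed group sizes, discharge days and risks.

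This affects a secondary objective. The estimate of Day 28 mortality is outside the point.

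**What to change.** 1. **Schedule (Protocol 5, Appendix 1, SAP 4.2).** State that each discharged patient's records are searched for re-admission and death to 28 days after discharge, and enter the last date searched in the eCRF.
2. **Analysis (SAP 9, endpoint 10.1).** Choose one of these:
   - Restrict the denominator to subjects with a complete 28-day window, judged by the last date searched and not by outcome. The crude proportion, its Clopper–Pearson interval and the chi-square test can then stay.
   - Keep all subjects discharged within the first 28 days and estimate 28-day cumulative incidence from discharge, censored at the last date searched, with death before re-admission as a competing event. Gray's test would then replace the chi-square test.
3. **Reporting.** Give the number of subjects with incomplete windows, overall and by baseline severity group.

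The cost is one eCRF date, a further look at records that sites already hold, and a few lines of SAP text. Under the first option, a few late admissions may drop out of this endpoint at the interim analysis.

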This is a non-interventional, observational study where no formal samples size calculation is to be performed. It is anticipated that at least 450 adults with COVID-19 and treated with Remdesivir could be recruited across centres from NEAT ID Network.

6. General Considerations

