7.2 Demographic and baseline variables

The baseline patients' characteristics of the full analysis population will be described globally and according to the Ordinal Scale (ORDSC) clinical status at baseline (score 2 vs 3-4 vs 5)

and will be presented in a summary table. The summary statistics will be produced in accordance with section 7. Non-parametric Kruskal-Wallis test will be used to compare continuous variable between the 3 groups and Chi-square test for categorical variables. P-values will be two-tailed with a significant level at 5%.

This table will be structured as follows:

8. Efficacy Analyses

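### The chi-square test fixed for outcomes after re-admission (endpoints 10.2 and 10.3) has no small-sample alternative, so its exploratory P-values may be unreliable if re-admissions are few

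*SAP*

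**What the plan says.** SAP section 9 (Other Analyses) covers endpoints 10.1 to 10.3 together. It summarises them by baseline ordinal score (2, 3-4, 5) and adds: "Chi square test will be used to compared the 3 groups". The P-values are two-tailed at 5%.

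The denominators differ. Endpoint 10.1 uses every patient discharged by Day 28. The other two endpoints use a much narrower set: "For 10.2 and 10.3, the analysis population will be all re-admitted subjects".

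SAP section 7.2 applies the same test to the baseline table: "Chi-square test for categorical variables".

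The SAP names no Fisher-type or other exact test, no minimum expected count and no fallback rule. For the same re-admission proportions, section 9 does plan exact Clopper-Pearson intervals.

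On numbers, SAP section 5 says only that "It is anticipated that at least 450 adults with COVID-19 and treated with Remdesivir could be recruited" and that "no formal samples size calculation is to be performed". Neither document gives a re-admission rate, a severity mix, or a rate of death or discharge after re-admission. SAP section 2 says there is no formal hypothesis to test.

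**The concern.** Endpoints 10.2 and 10.3 look at a subset of a subset: about 450 patients, then those discharged, then those who came back. That remainder is split three ways and cross-classified by a two-level outcome, which gives six cells. The chi-square P-value is a large-sample approximation and can be poor when expected counts are small.

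This is a stated rule, not an omitted detail. An analyst following the SAP would report the chi-square P-value whatever the counts. At stake is whether one or two deaths in a small severity group are reported as a significant difference when the exact calculation shows nothing of the kind.

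**Working it through.** The plan states no figure for this analysis, so there is none to reproduce.

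**Inputs from the documents.** 450 patients (SAP section 5); three groups, chi-square, two-tailed 5% (SAP section 9). A 3 x 2 table has 2 degrees of freedom, with critical value 5.99.

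**Assumptions (not in the documents).**
- 85% discharged by Day 28 and 5-10% of them re-admitted: 450 x 0.85 x 0.05 = 19 and 450 x 0.85 x 0.10 = 38. I therefore take 20 and 40 re-admissions.
- Death after re-admission in 10% or 20%. The table for discharge is the same if every re-admitted patient either dies or is discharged.
- Severity split 5/70/25%, 10/75/15%, or near-equal groups.

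**Formulas.** Expected deaths in a group = group size x death rate. True size = the probability, summed over all possible 3 x 2 tables with fixed group sizes and one common death rate, that the test gives P of 0.05 or less. FFH is the Fisher-Freeman-Halton exact test.

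| Groups | Death rate | Expected deaths per group | Chi-square size | FFH size |
|---|---|---|---|---|
| 1/14/5 | 10% | 0.1 / 1.4 / 0.5 | 9.4% | 2.6% |
| 1/14/5 | 20% | 0.2 / 2.8 / 1.0 | 7.9% | 2.0% |
| 2/28/10 | 10% | 0.2 / 2.8 / 1.0 | 6.4% | 3.5% |
| 2/28/10 | 20% | 0.4 / 5.6 / 2.0 | 5.2% | 4.1% |
| 2/15/3 | 10% | 0.2 / 1.5 / 0.3 | 6.1% | 1.4% |
| 2/15/3 | 20% | 0.4 / 3.0 / 0.6 | 5.8% | 2.7% |
| 4/30/6 | 10% | 0.4 / 3.0 / 0.6 | 6.7% | 3.4% |
| 4/30/6 | 20% | 0.8 / 6.0 / 1.2 | 4.7% | 4.0% |
| 7/7/6 | 10% | 0.7 / 0.7 / 0.6 | 1.9% | 0.7% |
| 7/7/6 | 20% | 1.4 / 1.4 / 1.2 | 4.2% | 2.2% |

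In the eight rows with unequal groups, 22 of the 24 expected death counts are below 5, and chi-square size runs from 4.7% to 9.4%.

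**One table by hand.** Groups 2/15/3, one death, in the group of 2. The overall rate is 1/20 = 0.05, so expected deaths are 0.10, 0.75 and 0.15. Each group contributes (observed - expected)^2 / (expected x 0.95):
- 0.81/0.095 = 8.53
- 0.5625/0.7125 = 0.79
- 0.0225/0.1425 = 0.16

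The sum is 9.47 on 2 degrees of freedom, so P = exp(-9.47/2) = 0.009. Under no difference, the one death falls in the group of 2 with probability 2/20 = 0.10, which is the least likely of the three placements, so the exact P is 0.10. Similarly, groups 2/30/6 with deaths 1/1/0 give chi-square P = 0.014 and exact P = 0.125.

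**When chi-square would be safe for 10.2 and 10.3.** With a 10/75/15% split, the smallest expected count is R x 0.10 x rate, where R is the number re-admitted. It reaches 5 at R = 100 for a 50% rate, 250 for 20% and 500 for 10%. With equal thirds it reaches 5 at R = 30 for 50% and R = 75 for 20%.

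**Endpoint 10.1.** The denominator is 450 x 0.85 = 382.5. With a 10/75/15% split, expected re-admissions per group are 1.9/14.3/2.9 at a 5% rate and 5.7/43.0/8.6 at 15%. Chi-square is doubtful in the first case and adequate in the second.

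**The case against.** - **The inflation is modest and depends on the split.** This stands. The 9.4% needs a group of exactly one patient. At 40 re-admissions with the same split, size is 6.4% and 5.2%. If group membership at 20 re-admissions is drawn at random in 5/70/25% proportions instead of being fixed, size is about 6.3% and 5.5%. With near-equal groups the test is conservative. A reader might infer that the chi-square P-value is simply invalid, or that false positives run at 8-10%; the documents give no rates that would support either statement.
- **Everything rests on assumed rates.** This also stands, and few re-admissions must be read as a condition. Sparse cells nevertheless persist over a wide range: with 10/75/15% or 5/80/15% splits, every scenario from 2% to 20% re-admission leaves 2 to 6 of the 6 expected counts below 5.
- **The chance of no deaths does not favour the exact test.** This stands. With 20 re-admissions and 10% deaths, 0.9^20 = 12% of samples have none and chi-square cannot be computed, but the exact test then returns P = 1 and is equally uninformative.
- **The exact intervals already planned are enough.** This stands in part. They describe each proportion, while the P-value compares three groups, so the two are not strictly inconsistent. But section 9 still calls for the P-value at 5%.
- **The analyses are exploratory.** True, and it limits the importance of the point. It does not make a misleading P-value harmless in a results table.

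**Conclusion.** The point holds for endpoints 10.2 and 10.3: the SAP fixes a large-sample test for a table likely to be sparse and provides no alternative. With 20-40 re-admissions, 10-20% deaths and unequal groups, true size is about 5-9% against a nominal 5%; with near-equal groups at 20 re-admissions it is about 2-4%. The practical risk lies more in single tables, where P = 0.009 can stand for an exact 0.10. All of this depends on the assumed re-admission, severity and death rates.

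A reader might extend the criticism to 10.1 and to rare rows of Table 1 such as pregnancy, HIV or dementia. The documents do not support that as a general claim: 10.1 uses everyone discharged within 28 days, and no prevalence is given for the Table 1 rows. For these the point is conditional on the counts observed.

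The importance is low. Only exploratory P-values are affected; Day 28 mortality is analysed by other methods.

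**What to change.** Add one sentence to SAP section 9, with a cross-reference in section 7.2: use the Fisher-Freeman-Halton exact test for endpoints 10.2 and 10.3, and for endpoint 10.1 or any categorical row of Table 1 in which an expected count is below 5; otherwise keep chi-square. Expected counts come from the table margins, so the rule can be applied without looking at the group comparison.

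No new data are needed. The cost is conservatism: the exact test's true size was 0.7% to 4.1% in the table above, and as low as 0.03% in a more extreme case (groups 7/7/7, 5% deaths), so it will have little power with few events. An acceptable alternative for 10.2 and 10.3 is to drop the P-value and report counts with the exact intervals already planned.
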